6.4. Visit 02 Baseline (Day 0)

Participants who continue to meet all inclusion/exclusion criteria after screening will present to the clinic for the baseline visit. The baseline visit will be performed within 30 days of the screening visit. However, the investigator will review, date and initial the screening laboratory assessments to confirm participant eligibility for study participation prior to the baseline visit procedures. Therefore, adequate time must be provided for the laboratory results to be received from the central laboratory. The investigator or designee will again review the study inclusion/exclusion criteria and participant medical history, confirming that the participant meets criteria for study participation before randomization.

The following procedures will be performed at the baseline visit (this visit may take about 4 hours):

- Review Inclusion/Exclusion criteria.
- Obtain a medical, family, and neurological history to assess for possible exclusionary conditions. Medical histories should include baseline symptoms, ongoing illnesses, other chronic conditions, surgical history, review of currently used medications, as well as any other important information that may affect the conduct of the study. See section 7.1.3.

- Review concomitant medications, including all nutritional, herbal and alternative therapies. See section 7.1.4.
- Review interval medical history.
- Review adverse events.
- Perform vital sign measurements: blood pressure (systolic and diastolic), heart rate (beats/minute), and body temperature (°C). See section 7.1.6.
- Record weight (kg) and Body Mass Index (BMI).
- Perform an abbreviated Physical Examination, including visual field and fall risk assessment.
- Perform Functional and Mobility testing (6MWT, TUG, ABC Scale). See section 7.1.11.
- Perform nerve conduction studies. See section 7.1.13.
- Perform distal thigh skin biopsy. See section 7.1.14.
- Collect blood samples for routine hematology panel blood, basic metabolic panel, topiramate level and DNA analysis (OPTIONAL). See section 7.1.12.
- Collect urine for a urine pregnancy test (pregnancy test for women of child-bearing potential only).
- For women of childbearing potential and sexually active males, review acceptable birth control methods that must be used during the study.
- Perform subject randomization via interactive voice response system (IVRS) and/or interactive web response system (IWRS). See section 4.4.5.
- Dispense study drug.
- Instruct subject about correct administration and titration of study drug. See section 5.3.2.
- Instruct subject to bring unused study drug to each study visit, and to immediately report any AEs to the Investigator or Coordinator.
- Administer the *Neuropathy Total Symptom Score-6* (NTSS-6) to the subject. See section 7.1.9.
- Administer the *Brief Pain Inventory – Diabetic Neuropathy* (BPI-DN) BPI-DN. See section 7.1.9.
- Perform clinical assessment for suicide ideation with the *Columbia-Suicide Severity Rating Scale* (C-SSRS). See section 7.1.15.
- Complete the Rapid Assessment of Physical Activity (RAPA) Survey. See section 7.1.17.

6.5. Visit 03 Week 16 (± 7 days)

This safety follow-up visit will occur within ± 7 days of the targeted visit date. The following procedures will be performed at the Week 16 visit (this visit may take about 3 hours):

- Review interval medical history.
- Review adverse events.
- Review concomitant medications, including all nutritional, herbal and alternative therapies. See section 7.1.4.
- Perform vital sign measurements: blood pressure (systolic and diastolic), heart rate (beats/minute), and body temperature (°C). See section 7.1.6.
- Record weight (kg) and Body Mass Index (BMI).
- Record waist circumference (cm). See section 7.1.7.
- Perform an Abbreviated Physical Examination including visual field examination and assessment for fall risk.

- Administer the *Utah Early Neuropathy Scale* (UENS). See section 7.1.10.
- Collect blood samples for safety monitoring laboratory assessments including basic metabolic panel, CBC and serum pregnancy test (pregnancy test for women of child-bearing potential only). (Refer to University of Rochester Medical Center Lab Manual for sample handling and processing requirements). See section 7.1.12.
- Dispense study drug.
- Perform study drug reconciliation and container collection.
- Assess study drug compliance.
- Administer the *Neuropathy Total Symptom Score-6* (NTSS-6) to the subject. See section 7.1.9.
- Administer the *Brief Pain Inventory – Diabetic Neuropathy* (BPI-DN) BPI-DN. See section 7.1.9.
- Administer the *Norfolk Quality of Life-Diabetic Neuropathy scale* (NQOL-DN). See section 7.1.19.
- Perform clinical assessment for suicide ideation with the *Columbia-Suicide Severity Rating Scale* (C-SSRS). See section 7.1.15.

6.6. Visit 04 Week 32 (\pm 7 days)

The follow-up visit will take place within \pm 7 days of the targeted visit date. The following procedures will be performed at the Week 32 evaluation visit (this visit may take about 4 hours):

- Review interval medical history.
- Review adverse events.
- Review concomitant medications, including all nutritional, herbal and alternative therapies. See section 7.1.4.
- Perform vital sign measurements: blood pressure (systolic and diastolic), heart rate (beats/minute), and body temperature ($^{\circ}$ C). See section 7.1.6.
- Record weight (kg) and Body Mass Index (BMI).
- Record waist circumference (cm). See section 7.1.7.
- Perform an abbreviated Physical Examination, including visual field and fall risk assessment.
- Administer the *Utah Early Neuropathy Scale* (UENS). See section 7.1.10.
- Perform Nerve Conduction Studies (NCS). See section 7.1.13.
- Perform distal thigh skin biopsy. See section 7.1.14.
- Collect blood samples for OGTT, CBC, fasting basic metabolic panel, fasting insulin, fasting lipid panel, HgbA1C, topiramate level and serum pregnancy test for women of child-bearing potential only. See section 7.1.12.
- Perform Functional and Mobility testing (6MWT, TUG, ABC Scale). See section 7.1.11.
- Dispense study drug.
- Perform study drug reconciliation and container collection.
- Assess study drug compliance.

- Administer the *Neuropathy Total Symptom Score-6* (NTSS-6) to the subject. See section 7.1.9.
- Administer the *Brief Pain Inventory – Diabetic Neuropathy* (BPI-DN) BPI-DN. See section 7.1.9.
Administer the *Norfolk Quality of Life-Diabetic Neuropathy scale* (NQOL-DN). See section 7.1.19.
- Perform clinical assessment for suicidal ideation with the *Columbia-Suicide Severity Rating Scale* (C-SSRS). See section 7.1.15.
- Complete the Rapid Assessment of Physical Activity (RAPA) Survey. See section 7.1.17.

6.7. Visit 05 Week 48 (± 7 days)

This safety follow-up visit will occur within ± 7 days of the targeted visit date. The following procedures will be performed at the Week 48 evaluation visit (this visit may take about 3 hours):

- Review interval medical history.
- Review adverse events.
- Review concomitant medications, including all nutritional, herbal and alternative therapies. See section 7.1.4.
- Perform vital sign measurements: blood pressure (systolic and diastolic), heart rate (beats/minute), and body temperature (°C). See section 7.1.6.
- Record weight (kg) and Body Mass Index (BMI).
- Record waist circumference (cm). See section 7.1.7.
- Perform an abbreviated Physical Examination, including visual field and fall risk assessment.
- Collect blood samples for safety monitoring laboratory assessments including basic metabolic panel, CBC and serum pregnancy test (pregnancy test for women of child-bearing potential only). See section 7.1.12.
- Dispense study drug.
- Perform study drug reconciliation and container collection.
- Assess study drug compliance.
- Administer the *Neuropathy Total Symptom Score-6* (NTSS-6) to the subject. See section 7.1.9.
- Administer the *Brief Pain Inventory – Diabetic Neuropathy* (BPI-DN) BPI-DN. See section 7.1.9.
- Administer the *Utah Early Neuropathy Scale* (UENS). See section 7.1.10.
- Administer the *Norfolk Quality of Life-Diabetic Neuropathy scale* (NQOL-DN). See section 7.1.19.
- Perform clinical assessment for suicidal ideation with the *Columbia-Suicide Severity Rating Scale* (C-SSRS). See section 7.1.15.

6.8. Visit 06 Week 64 (± 7 days)

The follow-up visit will take place within ± 7 days of the targeted visit date. The following procedures will be performed at the Week 64 evaluation visit (this visit may take about 4 hours):

NN108 Topiramate as a Disease Modifying Therapy for CSPN

Version 8.0

Version date 8/8/2018

- Review interval medical history.
- Review adverse events.
- Review concomitant medications, including all nutritional, herbal and alternative therapies. See section 7.1.4.
- Perform vital sign measurements: blood pressure (systolic and diastolic), heart rate (beats/minute), and body temperature (°C). See section 7.1.6.
- Record weight (kg) and Body Mass Index (BMI).
- Record waist circumference (cm). See section 7.1.7.
- Perform an abbreviated Physical Examination, including visual field and fall risk assessment.
- Administer the *Utah Early Neuropathy Scale* (UENS). See section 7.1.10.
- Perform Functional and Mobility testing (6MWT, TUG, ABC Scale). See section 7.1.11.
- Perform Nerve Conduction Studies (NCS). See section 7.1.13.
- Perform distal thigh skin biopsy. See section 7.1.14.
- Collect blood samples for OGTT, CBC, basic metabolic panel, fasting insulin, fasting lipid panel, HgbA1C, topiramate level and serum pregnancy test for women of child-bearing potential only. See section 7.1.12.
- Dispense study drug.
- Perform study drug reconciliation and container collection.
- Assess study drug compliance.
- Administer the *Neuropathy Total Symptom Score-6* (NTSS-6) to the subject. See section 7.1.9.
- Administer the *Brief Pain Inventory – Diabetic Neuropathy* (BPI-DN) BPI-DN. See section 7.1.9.
- Administer the *Norfolk Quality of Life-Diabetic Neuropathy scale* (NQOL-DN). See section 7.1.19.
- Perform clinical assessment for suicidal ideation with the *Columbia-Suicide Severity Rating Scale* (C-SSRS). See section 7.1.15.
- Complete the Rapid Assessment of Physical Activity (RAPA) Survey. See section 7.1.17.

6.9. Visit 07 Week 80 (± 7 days)

This safety follow-up visit will occur within ± 7 days of the targeted visit date. The following procedures will be performed at the Week 80 visit (this visit may take about 3 hours):

- Review interval medical history.
 - Review adverse events.
 - Review concomitant medications, including all nutritional, herbal and alternative therapies. See section 7.1.4.
 - Perform vital sign measurements: blood pressure (systolic and diastolic), heart rate (beats/minute), and body temperature (°C). See section 7.1.6.
 - Record weight (kg) and Body Mass Index (BMI).
 - Record waist circumference (cm). See section 7.1.7.
 - Perform an abbreviated Physical Examination, including visual field and fall risk assessment.
- Administer the *Utah Early Neuropathy Scale* (UENS). See section 7.1.10.

- Collect blood samples for safety monitoring laboratory assessments including basic metabolic panel, CBC, and serum pregnancy test (pregnancy test for women of child-bearing potential only). See section 7.1.12.
- Dispense study drug.
- Perform study drug reconciliation and container collection.
- Assess study drug compliance.
- Administer the *Neuropathy Total Symptom Score-6* (NTSS-6) to the subject. See section 7.1.9.
- Administer the *Brief Pain Inventory – Diabetic Neuropathy (BPI-DN)* BPI-DN. See section 7.1.9.
- Administer the *Norfolk Quality of Life-Diabetic Neuropathy scale* (NQOL-DN). See section 7.1.19.
- Perform clinical assessment of suicidal ideation with the *Columbia-Suicide Severity Rating Scale* (C-SSRS). See section 7.1.15.

6.10. Visit 08 Week 96 Termination (± 7 days)

The final study treatment visit will occur 96 weeks following baseline. All assessments performed at the evaluation visits will take place. The investigator will perform a complete physical examination. All study drug and study drug packages will be collected from the subject at this visit and a final assessment of study drug compliance will be calculated. The Week 96 visit will occur within ± 7 days of the targeted visit date.

The following procedures will be performed at the Week 96 visit (this visit may take about 5 hours):

- Review interval medical history.
- Review adverse events.
- Review concomitant medications, including all nutritional, herbal and alternative therapies. See section 7.1.4.
- Perform vital sign measurements: blood pressure (systolic and diastolic), heart rate (beats/minute), and body temperature (°C). See section 7.1.6.
- Record weight (kg) and Body Mass Index (BMI).
- Record waist circumference (cm). See section 7.1.7.
- Perform a general medical and detailed neuromuscular physical examination. See section 7.1.5.
- Administer the *Utah Early Neuropathy Scale* (UENS). See section 7.1.10.
- Perform Functional and Mobility testing (6MWT, TUG, ABC Scale). See section 7.1.11.
- Perform Nerve Conduction Studies (NCS). See section 7.1.13.
- Perform distal thigh skin biopsy. See section 7.1.14.
- Collect blood samples for fasting basic metabolic panel, CBC, fasting insulin, fasting lipid panel, two-hour OGTT, topiramate level and HgbA1C. See section 7.1.12.
- Perform study drug reconciliation and container collection.
- Assess study drug compliance.
- Administer the *Neuropathy Total Symptom Score-6* (NTSS-6) to the subject. See section 7.1.9.
- Administer the *Brief Pain Inventory – Diabetic Neuropathy (BPI-DN)* BPI-DN. See section 7.1.9.
- Administer the *Norfolk Quality of Life-Diabetic Neuropathy scale* (NQOL-DN). See section 7.1.19.

- Perform clinical assessment for suicidal ideation with the *Columbia-Suicide Severity Rating Scale* (C-SSRS). See section 7.1.15.
- Complete the Rapid Assessment of Physical Activity (RAPA) Survey. See section 7.1.17.

6.11. Visit 09 Safety Assessment

A safety call or visit will occur 4 weeks (+/- 7 days) following the last dose of study drug. The following procedures will be performed at the safety assessment (this visit may take up to 2 hours).

If the Site PI determines a Safety Call is appropriate for final safety assessment, the following information should be collected;

- Review interval medical history.
- Review adverse events.
- Review concomitant medications, including all nutritional, herbal and alternative therapies. See section 7.1.4.

If the Site PI determines a Safety Visit is required for either a final safety assessment or an unscheduled safety visit the following additional procedures can be performed (optional safety data based on clinical judgement of site PI):

- Review interval medical history.
- Review adverse events.
- Review concomitant medications, including all nutritional, herbal and alternative therapies. See section 7.1.4.
- Perform vital sign measurements: blood pressure (systolic and diastolic), heart rate (beats/minute), and body temperature (°C). See section 7.1.6.
- Record weight (kg) and Body Mass Index (BMI).
- Perform a general medical and detailed neuromuscular physical examination. See section 7.1.5.
- Collect blood samples for basic metabolic panel and CBC. See section 7.1.14.
- Perform clinical assessment for suicidal ideation with the *Columbia-Suicide Severity Rating Scale* (C-SSRS). See section 7.1.15.

6.12. Early Termination Visit ($\leq 30 \pm 7$ days)

The following procedures will be performed at the early termination visit (this visit may take about 5 hours):

- Review interval medical history.
- Review adverse events.
- Review concomitant medications, including all nutritional, herbal and alternative therapies. See section 7.1.4.
- Perform vital sign measurements: blood pressure (systolic and diastolic), heart rate (beats/minute), and body temperature (°C). See section 7.1.6.
- Record weight (kg) and Body Mass Index (BMI).
- Record waist circumference (cm). See section 7.1.7.
- Perform a general medical and detailed neuromuscular physical examination. See section 7.1.5.
- Perform Functional and Mobility testing (6MWT, TUG, ABC Scale). See section 7.1.11.

- Perform Nerve Conduction Studies (NCS). See section 7.1.13.
- Perform distal thigh skin biopsy. See section 7.1.14.
- Collect blood samples for fasting basin metabolic panel, CBC, fasting insulin, fasting lipid panel, topiramate level, two-hour OGTT and HgbA1C. See section 7.1.12.
- Perform study drug reconciliation.
- Administer the *Neuropathy Total Symptom Score-6* (NTSS-6) to the subject. See section 7.1.9.
- Administer the *Brief Pain Inventory – Diabetic Neuropathy* (BPI-DN) BPI-DN. See section 7.1.9.
- Administer the *Utah Early Neuropathy Scale* (UENS). See section 7.1.10.
- Administer the *Norfolk Quality of Life-Diabetic Neuropathy scale* (NQOL-DN). See section 7.1.16.
- Perform clinical assessment for suicidal ideation with the *Columbia-Suicide Severity Rating Scale* (C-SSRS). See section 7.1.15.
- Complete the Rapid Assessment of Physical Activity (RAPA) Survey. See section 7.1.17.

6.13. Early Termination and Premature Withdrawal

Subjects have the right to withdraw from the study at any time without prejudice. The site Investigator may withdraw study drug from a subject in the study in the event of intercurrent illness, adverse events, other reasons concerning the health or well-being of the subject or other administrative reasons. Early termination will be implemented in the case of emergency disclosure of drug treatment (i.e., unblinding). **NOTE: All efforts should be made by study staff to encourage subjects to return for follow-up visit(s). If a subject withdraws consent from the study in writing, no further contact can be made.**

A subject may discontinue study medication for the following reasons:

Administrative

1. Withdrawal of consent
2. Request of Sponsor or Principal Investigator
3. Request of primary care physician
4. Pregnancy
5. Subject deemed lost to follow up/failure to return
6. Termination of study
7. Other

Adverse Event

1. Worsening of the disease under study
2. Worsening of pre-existing disease (other than disease under study)
3. Intercurrent illness
4. Death
5. Major/clinically significant alteration in laboratory values after beginning study drug
6. Suicidality based on the C-SSRS
7. Other adverse event

In the event a participant discontinues study medication for any reason, every effort should be made to complete the evaluation visits at week 32, 64, and 96. An early termination visit should be completed for all participants who are unable or unwilling to complete additional evaluation visits. If a subject is unable to return to the site, or refuses to complete all termination visit procedures, any reasonable study procedures to which the subject consents will be completed.

Should a scheduled in-person visit be impossible, conduct as many of the verbal assessments as possible, with special emphasis on obtaining information on possible AEs, and arrange for return of study drug. Every effort will be made to determine the subject's health status at withdrawal.

Reasons for early termination of the subject prior to completion of the study must be stated in the CRF and in the site source documentation for all study subjects who were enrolled in the study. The CCC and the IMM must be informed within 24 hours of all study subjects who are withdrawn due to an adverse event.

6.13.1. Premature Drug Discontinuation

Subjects who prematurely discontinue study drug will be questioned regarding reasons for discontinuation. Subjects will be encouraged to restart study drug following the guidelines in section 6.12.2.

6.13.2. Restarting Study Drug after Premature Drug Discontinuation

Subjects who discontinue study drug for less than one week will be asked to restart at the prior dose. Those who failed to take study drug for 1-7 days will be asked to restart at the previous dose. Those not having taken study drug for 8-14 days will restart at half of the prior dose. Those not having taken study drug for 15 days or more will restart the titration. Those who discontinued due to an adverse event will restart at a dose lower than the maximally tolerated dose and titrate to that dose.

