4.4.5. Randomization/Treatment Assignment

Randomization to study treatment (either topiramate or matching over-encapsulated placebo) will occur using an interactive web response system (IWRS). Online randomization will follow confirmation of eligibility and completion of all required baseline procedures. Randomization codes will be constructed using random permuted blocks to assure balanced randomization over time with stratification by BMI. BMI of 30.0 will serve as stratification cutoffs reflecting anticipated median values.

Following randomization, subjects will be given a supply of study drug with instructions to take the study drug twice daily using a 2-week dose escalation schedule. Subjects will titrate to two 25mg tablets twice daily, or the maximally tolerated dose.

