5.3. Formulation and Packaging

Study drug, or matching placebo, will be provided in labeled packages with sufficient product for study subjects to take four capsules daily for 16 weeks, with sufficient overage in each package to allow for anticipated variation in visit scheduling. Four 132-count bottles will be provided, permitting for 14 days of overage. Each study test article packet will be labeled with the following information:

- Name of Sponsor
- Name and address of study drug distribution center
- Study number and IND number
- Unique drug package number
- Drug treatment label (each kit will list either 25 mg topiramate or placebo)
- Route of administration
- Quantity of dose unit
- Directions for use
- Storage conditions
- Space for investigator name, telephone, dispensing date and subject number
- Space for study subject identifier
- Label statement "Caution: New Drug-Limited by federal law to investigational use"

Label statement “Caution: Keep out of reach of children”

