5.3.2. Titration Schedule and Dose Adjustments

Subjects randomized to the topiramate arm will start 25mg topiramate once daily in the evening. On day 4 following randomization a morning dose of 25 mg will be added. On day 8 following randomization an additional 25 mg tablet will be added in the evening, and on day 12 a second morning dose will be added so that the subject will be taking a total of 50mg twice daily. Subjects who experience an adverse event during the dose titration may continue at the highest tolerated dose for one week prior to an additional attempt to increase to the targeted dose. Those who are tolerant of a lower dose but intolerant of the target dose will continue on the highest tolerated dose. Results will be analyzed in an intent to treat fashion. If a subject develops a treatment related adverse event, the dose may be lowered at the discretion of the site PI in order to establish a lower maximally tolerated dose. Those who have an adverse event and are unable to continue medication will undergo a termination visit.

In accordance with local regulatory requirements, the investigator, designated site staff, or head of the medical institution (where applicable) must document the amount of investigational product dispensed and/or administered to study subjects, the amount received from the central pharmacy, and the amount destroyed upon completion of the study. An investigator is responsible for ensuring product accountability records are maintained throughout the course of the study. The inventory will include details of *topiramate* received and dispensed to subjects, batch, and ID numbers. All unused *capsules* must be kept until reconciliation of delivery records with accountability logs by the monitor. After the monitor has performed accountability, the site will be instructed by the DCC or designee to either destroy the remaining study drug or return it to the

Central Pharmacy or manufacturer. An accounting must be made of any drug deliberately or accidentally destroyed. Discrepancies between the amount of topiramate received and dispensed drug must be reconciled.

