6.13.3. Missed Doses

Subjects who miss a dose will continue the planned dosing schedule and will not supplement the next dose with that which was missed.

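### For some patients the restart rules in 6.13.2 call for a dose that 25 mg units cannot make up, and after an adverse-event stop two of the rules contradict each other with no stated precedence.

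*Combined protocol and SAP*

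**What the plan says.** Section 6.13.2 gives restart instructions by time off drug:

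- Up to a week: "Subjects who discontinue study drug for less than one week will be asked to restart at the prior dose". The next sentence repeats this for gaps of 1-7 days. The two overlap but give the same dose.
- 8-14 days: "Those not having taken study drug for 8-14 days will restart at half of the prior dose".
- 15 days or longer: "Those not having taken study drug for 15 days or more will restart the titration".
- A final sentence covers anyone who stopped because of an adverse event. They resume below their maximally tolerated dose and work up to it. No gap length is attached, and nothing says whether this sentence or the duration rules govern.

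On supply, section 5.3 says "each kit will list either 25 mg topiramate or placebo" and provides enough product "for study subjects to take four capsules daily for 16 weeks". Section 4.4.5 describes the product as "either topiramate or matching over-encapsulated placebo". No smaller strength, splitting instruction or rounding rule appears.

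On dose levels, section 5.3.2 builds up in 25 mg steps to 100 mg/day and allows patients to remain lower: "Those who are tolerant of a lower dose but intolerant of the target dose will continue on the highest tolerated dose".

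Section 6.13.1 refers sites to section 6.12.2 for restarting. No such section exists; 6.12 is the early termination visit.

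**The concern.** A restart rule has to yield one dose that the site can dispense. Two features of 6.13.2 prevent that for some patients. Halving a dose made of an odd number of 25 mg units leaves half a unit. And an adverse-event stop also falls into one of the duration bands, so two sentences apply to the same patient.

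The second matters more. After a short stop for an adverse event, one sentence returns the patient to the dose they were taking, while another requires less than they can tolerate. Sites could reasonably act on either, and the choice bears on patient safety. The analysis follows randomized assignment, so whatever dosing results stays in the comparison.

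**Working it through.** **Inputs.** Unit strength 25 mg and four capsules daily at target (5.3). Target 100 mg/day (5.1). Titration levels 25, 50, 75 and 100 mg/day, starting at 25 and rising on days 4, 8 and 12 (5.3.2). Restart rules from 6.13.2.

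**The plan's own figure.** 4 capsules × 25 mg = 100 mg/day, which matches the target.

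**Step 1: can half the prior dose be given?** Half dose = prior daily dose / 2; units needed = half dose / 25.

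| Prior dose (mg/day) | Half (mg/day) | Units needed | Whole number? |
|---|---|---|---|
| 100 | 50 | 2 | yes |
| 75 | 37.5 | 1.5 | no |
| 50 | 25 | 1 | yes |
| 25 | 12.5 | 0.5 | no |

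Two of the four dose levels fail. This halves the daily total, which is the lenient reading. If each intake were halved separately, 50 mg/day (25 + 25) would also fail, at 12.5 + 12.5, while 100 mg/day (50 + 50) would still work.

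**Step 2: does the adverse-event sentence agree with the duration rules?** Let P be the prior dose and M the maximally tolerated dose, with M no greater than P. That gives 10 combinations of the four levels. The adverse-event sentence requires a restart dose below M. The duration rules give P at 1-7 days, P/2 at 8-14 days, and 25 mg/day (the first titration step) at 15 days or more.

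| P / M (mg/day) | 1-7 days: P | 8-14 days: P/2 | 15+ days: 25 |
|---|---|---|---|
| 25 / 25 | conflict | 12.5, below M but not deliverable | conflict |
| 50 / 25 | conflict | 25, conflict | conflict |
| 50 / 50 | conflict | 25, agrees | agrees |
| 75 / 25 | conflict | 37.5, conflict and not deliverable | conflict |
| 75 / 50 | conflict | 37.5, below M but not deliverable | agrees |
| 75 / 75 | conflict | 37.5, below M but not deliverable | agrees |
| 100 / 25 | conflict | 50, conflict | conflict |
| 100 / 50 | conflict | 50, conflict | agrees |
| 100 / 75 | conflict | 50, agrees | agrees |
| 100 / 100 | conflict | 50, agrees | agrees |

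- At 1-7 days, 10 of 10 combinations conflict, because P is never below M.
- At 8-14 days, 4 of 10 conflict. Of the other six, three call for an undeliverable dose and three work.
- At 15 days or more, only the four rows with M = 25 fail, because no unit dose lies below 25 mg.

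**Step 3: what happens after the restart dose?** The 15-day rule leads into the titration, and the adverse-event sentence says to work up to the tolerated dose. The 8-14 day rule gives a starting dose and no next step, interval or end point.

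**The case against.** The best reply is that the ordinary case works. A patient at 100 mg/day whose interruption has nothing to do with an adverse event has a clear restart dose in every band, and half of 100 mg is one capsule twice daily. That stands. It would be wrong to infer that sites cannot apply 6.13.2 at all.

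On precedence, the adverse-event sentence comes last and covers a specific group, so many readers would let it override the general rules. That is reasonable, but the text does not say so.

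On the 25 mg case, 5.3.2 provides a termination visit for those unable to continue medication. That does not help someone who does tolerate 25 mg/day and wishes to resume.

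Three stronger readings are tempting and should be set aside:

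- *A 10-day gap leaves a 100 mg/day patient on half dose permanently, while a 15-day gap leads back to target.* This compares two different patients and reads a ceiling into silence. Section 4.4.5 says patients titrate to target or the maximally tolerated dose. The defect is a missing step-up instruction.
- *Restarting the titration forces a patient with a lower tolerated dose up to 100 mg/day.* Sections 4.4.5 and 5.3.2 both let the titration end at the tolerated dose.
- *The missed-dose rule contradicts the restart rule after a week off drug during titration.* Section 6.13.3 says "Subjects who miss a dose will continue the planned dosing schedule" and concerns a single dose. A gap of several days falls under 6.13.2.

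**Conclusion.** The rules are wrong as written, for identifiable groups of patients. Two defects are established:

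- The 8-14 day rule cannot be carried out at 25 or 75 mg/day. The adverse-event rule likewise cannot be carried out when the tolerated dose is 25 mg/day.
- The adverse-event sentence contradicts the 1-7 day rule in every combination examined and the 8-14 day rule in 4 of 10.

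The missing step back up after 8-14 days and the dead reference in 6.13.1 are lesser points.

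This rests on two assumptions. Doses are whole 25 mg units, since no splitting is described; and the maximally tolerated dose does not exceed the dose being taken at the stop. The second might not hold for someone stopped partway through titration.

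The counts are of dose levels and combinations, not of patients. The documents give no frequency for dosing below target, for gaps of 8-14 days or for adverse-event restarts, so the number affected cannot be derived. A reader might infer a diluted treatment contrast. The documents do not support that: dosing up to the tolerated level with intent-to-treat analysis is already the plan, and no effect on sample size, power or alpha is shown.

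**What to change.** The sponsor should reconcile 6.13.2 with 5.3 and 5.3.2, choosing the doses itself, so that:

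1. Every restart dose, from each of the four prior dose levels, is a whole number of 25 mg units, and the case of a 25 mg/day tolerated dose is addressed.
2. The text says which rule governs when an adverse-event stop also fits a duration band.
3. The text says whether, how and when the dose returns to the target or tolerated dose after an 8-14 day gap.
4. The cross-reference in 6.13.1 points to the restart section.

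A short table by prior dose, gap length and reason for stopping would be one convenient format; a few added sentences would also do. The cost is protocol wording and matching site instructions. Supply, visits and analysis need not change.
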